8.3 SAMPLE SIZE DETERMINATION AND RATIONALE

The sample size of 90 total subjects [60 subjects (30 subjects per arm) for the Randomized Phase and up to 30 subjects for the non-randomized, open-label phase] is selected on the basis of clinical judgment and not based on statistical power calculation. The number of subjects is deemed adequate to provide clinically meaningful descriptive results consistent with study objectives.

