## 2.7 Randomization

Part 1:

Subjects who are eligible to participate in the trial will be randomized 1:1 to one of the treatment groups via IWRS (Interactive Web Based Randomization System) at the Visit prior to IP administration. The randomization will be central and will use 1:1 ratio of Treatment groups

- Leronlimab 700mg SC weekly injection
- Placebo 0mg SC weekly injection

Part 2:

Randomization is not applicable for the open-label, single-arm portion (Part 2) of the study.

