## 4 SAMPLE SIZE

The sample size of 90 total subjects [60 subjects (30 subjects per arm) for the Randomized Phase and up to 30 subjects for the non-randomized, open-label phase] is based on clinical judgment. The number of subjects is deemed adequate to provide clinically meaningful descriptive results consistent with study objectives.

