## 9 STATISTICAL METHODS

### 9.1 GENERAL STATISTICAL CONSIDERATIONS

All statistical summaries and analyses will be performed using SAS® for Windows, version 9.4 or later.

Collected study data will be presented in subject data listings.

For continuous variables descriptive statistics (n, mean, standard deviation, median, minimum and maximum) will be presented by treatment group.

For categorical variables data summaries by treatment group will include frequency counts and percentages.

Formal treatment group comparisons will be made at the nominal two-sided 0.05 level of significance using the FAS and PP analysis sets. The 95% confidence intervals and p-values for comparing treatment groups will be computed.

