#### 9.2.4 Analysis of CCR5 Biomarkers that may Predict Activity of Leronlimab

To examine if monocyte/T cell CCR5 biomarker is predictive of leronlimab activity, the statistical significance of biomarker and treatment group interaction group will be assessed. The change from baseline to Week 14 in MRI-PDFF (and cT1) will be regressed on biomarker and treatment group and their interaction as covariables. The p-values for these effects will be presented:

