#### Summary of Biomarker as a Predictive Factor PART 1\*

**	p-value		
	Bio-marker	Treat-ment	Inter-action
Pro-inflammatory Biomarkers	0.xxx	0.xxx	0.xxx
IL-1 alpha	0.xxx	0.xxx	0.xxx
IL-1 beta	0.xxx	0.xxx	0.xxx
IL-6	0.xxx	0.xxx	0.xxx
RANTES (CCL5)	0.xxx	0.xxx	0.xxx
TNF-alpha	0.xxx	0.xxx	0.xxx
TNF-beta	0.xxx	0.xxx	0.xxx
CRP	0.xxx	0.xxx	0.xxx
Fibro Test			
Gamma-glutamyltransferase	0.xxx	0.xxx	0.xxx
Total bilirubin	0.xxx	0.xxx	0.xxx
Alpha-2-macroglobulin	0.xxx	0.xxx	0.xxx
Apolipoprotein A1	0.xxx	0.xxx	0.xxx
Haptoglobin.	0.xxx	0.xxx	0.xxx
ALT	0.xxx	0.xxx	0.xxx
Liver Function Tests / NASH Markers	0.xxx	0.xxx	0.xxx
Total Bilirubin	0.xxx	0.xxx	0.xxx
Direct Bilirubin	0.xxx	0.xxx	0.xxx
Alkaline Phosphatase (ALP)	0.xxx	0.xxx	0.xxx
Alanine Aminotransferase (ALT) (or SGPT)	0.xxx	0.xxx	0.xxx
Aspartate Aminotransferase (AST) (or SGOT)	0.xxx	0.xxx	0.xxx
Prothrombin Time (PT)	0.xxx	0.xxx	0.xxx
International Normalized Ratio (INR)	0.xxx	0.xxx	0.xxx
Albumin	0.xxx	0.xxx	0.xxx
Total Protein	0.xxx	0.xxx	0.xxx
Triglycerides	0.xxx	0.xxx	0.xxx
Cholesterol (Low density lipoprotein)	0.xxx	0.xxx	0.xxx
Cholesterol (High density lipoprotein)	0.xxx	0.xxx	0.xxx

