## STATISTICAL ANALYSIS PLAN (SAP) CD1-NASH-01

Protocol No. CD1-NASH-01	Revision No. Rev. 00	Effective Date: 17-Dec-2021
-----------------------------	-------------------------	--------------------------------

Creatine Kinase	0.xxx	0.xxx	0.xxx
Gamma-glutamyltransferase (GGT)	0.xxx	0.xxx	0.xxx
Serum CK-18	0.xxx	0.xxx	0.xxx

\*Programming Note 1: Repeat for Part 2 using Placebo from Part 1 in the statistical model

\*\*Programming Note2: Please adjust the list according to the actual lab data.

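### The Treatment p-value in the SAP 9.2.4 marker table comes from an interaction model with no stated marker centring or test type, so it may test the drug effect at a marker value of zero (minor)

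*SAP*

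**What the plan says.** SAP 9.2.4 sets out to learn whether a marker predicts response: "the statistical significance of biomarker and treatment group interaction group will be assessed". The change to Week 14 in MRI-PDFF (and cT1) is "regressed on biomarker and treatment group and their interaction as covariables. The p-values for these effects will be presented". The shell, titled "Summary of Biomarker as a Predictive Factor", has three p-value columns (Biomarker, Treatment, Interaction) and 28 named marker rows. GGT, total bilirubin and ALT each appear twice, so there are 25 distinct markers. Programming Note 1 adds: "Repeat for Part 2 using Placebo from Part 1 in the statistical model".

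The section does not state the marker's scale, any centring or transformation, whether the marker is a baseline level or a change, the type of test, or the marker value at which the treatment effect is read. The shell has no estimates or confidence intervals.

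The drug effect itself is tested in SAP 9.2.1, by an ANCOVA with no marker term.

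**The concern.** Once a model contains a marker-by-treatment product, the treatment term no longer describes the average drug effect. Its coefficient, or a Type III test of it, is the difference between arms for a subject whose marker equals zero. In the reference ranges printed in SAP 9.3.3, zero lies below the lower limit for AST, ALT, ALP and total bilirubin. Albumin, INR, prothrombin time and total protein cannot plausibly be near zero in a living subject. For such markers the test extrapolates well outside the data.

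At stake is a column of treatment p-values on the primary outcome and the first-listed secondary outcome. It may disagree with SAP 9.2.1 for purely arithmetical reasons. A row could be read as showing no drug effect once the marker is allowed for, or as showing an effect that is not there on average. With no estimate or interval printed, the reader could not detect either.

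**Working it through.** **Inputs from the documents.** Part 1 has "60 subjects (30 subjects per arm) for the Randomized Phase", and SAP 2.7 says: "The randomization will be central and will use 1:1 ratio of Treatment groups". The test level comes from SAP 9.1: "Formal treatment group comparisons will be made at the nominal two-sided 0.05 level of significance". Reference ranges are in SAP 9.3.3. There is no planned power to reproduce, because the sample size "is selected on the basis of clinical judgment and not based on statistical power calculation" (Protocol 8.3).

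**Assumptions.** The true effect is 0.74 SD, the size that 30 per arm detects with about 80% power. There is no interaction unless stated. Each reference range is read as mean ± 1.96 SD.

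**Formula.** Take change = b0 + b1·M + b2·T + b3·M·T. Then b2 is the arm difference at M = 0. In each arm the variance of the fitted value at M = 0 is (σ²/n)(1 + (mean/SD)²). Over two arms:

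SE(b2) = σ·√(2/n)·√(1 + (mean/SD)²).

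Centring removes the last factor.

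**Centred.** √(2/30) = 0.258, and 0.74/0.258 = 2.87. On 60 − 4 = 56 df (critical t 2.00) power is 80%.

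**Raw scale, reference ranges as the assumed spread.**

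| Marker | Mean | SD | Mean/SD | SE factor | Noncentrality | Power |
|---|---|---|---|---|---|---|
| AST 15–41 | 28 | 6.63 | 4.22 | 4.34 | 0.66 | 10% |
| ALP 34–104 | 69 | 17.9 | 3.86 | 3.99 | 0.72 | 11% |
| ALT, men 17–63 | 40 | 11.7 | 3.41 | 3.55 | 0.81 | 12–13% |
| Total bilirubin 0.2–0.9 | 0.55 | 0.179 | 3.08 | 3.24 | 0.88 | 14% |
| Direct bilirubin 0.0–0.2 | 0.10 | 0.051 | 1.96 | 2.20 | 1.30 | 25% |

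Simulation at 0.74 SD gave 9% for AST, 10% for ALP and 13% for total bilirubin. A repeat run came within about a percentage point. Centred power was 79–80%.

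**Wider spread.** Enrolled patients may vary more than the reference population. Spread the marker evenly from the lower reference limit to the eligibility limit (5 × ULN for enzymes, 1.3 mg/dL for total bilirubin). Raw-scale power becomes 24% (AST), 25% (ALP), 25% (ALT) and 20% (total bilirubin). Direct bilirubin has no eligibility limit; spread evenly over its reference range it gives 29%.

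**Other effect sizes.** At mean/SD = 4, effects of 0.72, 0.84 and 1.11 SD (80%, 90% and 99% power when centred) give raw-scale power of 10%, 12% and 18%.

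**High-CV markers.** With CV = SD/mean, the formula at 0.74 SD gives 51% at CV 1 and 71% at CV 2. For lognormal markers, simulation gives about 44–45% at CV 1, 54–57% at CV 1.5 and 61% at CV 2.

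**Opposite direction.** Suppose the average effect is zero and the interaction is 0.8 SD per marker SD. At mean/SD = 4 the effect at zero is −0.8 × 4 = −3.2, its SE is 0.258 × 4.12 = 1.06, and the ratio is about −3. Simulated at CVs of 0.1, 0.25 and 0.5, the raw Treatment test rejects in 75–82% of trials, against 6–7% centred.

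**Interaction column.** In every simulated trial its p-value was the same with and without centring.

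**The case against.** The strongest reply is that the SAP never says the markers are uncentred; that is inferred from silence. A sequential or Type II treatment test avoids the problem and keeps 76–79% power in simulation at a 0.72 SD effect. A change-from-baseline marker with mean/SD of 0.5 or less would inflate the standard error at most 1.12-fold. This stands: the defect is conditional on an unstated choice. It does not dispose of the point, because literal fitting of the stated model uses raw values, and that choice moves a printed p-value from about 80% power to about 10% for some markers.

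A reader might infer that a real drug effect would vanish in most rows. The documents do not support that. They give a reference range for only 7 of the 28 rows (total bilirubin twice, ALT twice, direct bilirubin, ALP, AST). The other 21 depend on CVs the documents do not supply, and skewed markers with high CVs would keep a fair share of their power.

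A reader might also infer that the Biomarker p-value always depends on how treatment is coded. That is true of a dummy-coded coefficient. It is not true of a Type III test with treatment as a class variable, which tests the average slope over the arms.

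Finally, the interaction is the declared target, the objective is exploratory, no decision in either document uses the Treatment column, and SAP 9.1.1 leaves final table formats to a separate document. All of this stands and limits the severity. SAP 9.2.4 also omits the baseline covariate that SAP 9.1.2 calls for; that is a separate matter.

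**Conclusion.** The point holds as a minor one. As specified, the Treatment p-value in SAP 9.2.4 has no defined meaning. On raw markers with coefficient or Type III tests it refers to a marker value of zero and can mislead in either direction. The loss of power is severe for AST, ALP and total bilirubin (about 9–13% by simulation, 10–14% by formula, against about 80% centred) and moderate for markers with a CV of 1 or more (roughly 45–70% kept). These figures assume a 0.74 SD effect, 30 per arm, no interaction and marker spreads that the documents do not state; the wider spreads above give 20–25% for those three markers. It cannot be said that the column will contradict the primary analysis, only that it may. The Interaction column and the SAP 9.2.1 ANCOVA are unaffected.

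**What to change.** In SAP 9.2.4, state that each continuous marker, log-transformed if skewed, is centred at its pooled mean before fitting, and name the type of test. A log transformation alone is not enough, since it only moves the reference point to a marker value of one unit. Alternatively, drop the Treatment and Biomarker columns, which the predictive question does not need.

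In either case, report the interaction coefficient with its 95% CI and the treatment difference at the marker's 25th and 75th percentiles. Apply the same rule to the Part 2 repeat.

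The cost is a sentence or two in the SAP, one line of code per model and a revised shell. No new data are needed, and the interaction test does not change if the marker is only centred. Log-transforming a skewed marker does change it, so that choice should be fixed before unblinding.

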#### Summary of Biomarker as a Predictive Factor PART 1\*

**	p-value		
	Bio-marker	Treat-ment	Inter-action
Pro-inflammatory Biomarkers	0.xxx	0.xxx	0.xxx
IL-1 alpha	0.xxx	0.xxx	0.xxx
IL-1 beta	0.xxx	0.xxx	0.xxx
IL-6	0.xxx	0.xxx	0.xxx
RANTES (CCL5)	0.xxx	0.xxx	0.xxx
TNF-alpha	0.xxx	0.xxx	0.xxx
TNF-beta	0.xxx	0.xxx	0.xxx
CRP	0.xxx	0.xxx	0.xxx
Fibro Test			
Gamma-glutamyltransferase	0.xxx	0.xxx	0.xxx
Total bilirubin	0.xxx	0.xxx	0.xxx
Alpha-2-macroglobulin	0.xxx	0.xxx	0.xxx
Apolipoprotein A1	0.xxx	0.xxx	0.xxx
Haptoglobin.	0.xxx	0.xxx	0.xxx
ALT	0.xxx	0.xxx	0.xxx
Liver Function Tests / NASH Markers	0.xxx	0.xxx	0.xxx
Total Bilirubin	0.xxx	0.xxx	0.xxx
Direct Bilirubin	0.xxx	0.xxx	0.xxx
Alkaline Phosphatase (ALP)	0.xxx	0.xxx	0.xxx
Alanine Aminotransferase (ALT) (or SGPT)	0.xxx	0.xxx	0.xxx
Aspartate Aminotransferase (AST) (or SGOT)	0.xxx	0.xxx	0.xxx
Prothrombin Time (PT)	0.xxx	0.xxx	0.xxx
International Normalized Ratio (INR)	0.xxx	0.xxx	0.xxx
Albumin	0.xxx	0.xxx	0.xxx
Total Protein	0.xxx	0.xxx	0.xxx
Triglycerides	0.xxx	0.xxx	0.xxx
Cholesterol (Low density lipoprotein)	0.xxx	0.xxx	0.xxx
Cholesterol (High density lipoprotein)	0.xxx	0.xxx	0.xxx

## STATISTICAL ANALYSIS PLAN (SAP) CD1-NASH-01

Protocol No. CD1-NASH-01	Revision No. Rev. 00	Effective Date: 17-Dec-2021
-----------------------------	-------------------------	--------------------------------

Creatine Kinase	0.xxx	0.xxx	0.xxx
Gamma-glutamyltransferase (GGT)	0.xxx	0.xxx	0.xxx
Serum CK-18	0.xxx	0.xxx	0.xxx

\*Programming Note 1: Repeat for Part 2 using Placebo from Part 1 in the statistical model

\*\*Programming Note2: Please adjust the list according to the actual lab data.

### 9.3 Analysis of Safety Data

#### 9.3.1 Extent of Exposure

The duration of exposure will be categorized as 0-2 weeks, 2-4 weeks, 4-8 weeks, 8-12 weeks, and >12 weeks. Actual categories will be specified at the time of reporting to adequately summarize the extent of exposure. The number and percentage of subjects in each category will be summarized using number (%) of subjects by treatment group and category.

Summary of Extent of Exposure  
N (%)

DURATION (WEEKS)	PLACEBO	LERONLIMAB 700MG	LERONLIMAB 350MG
0-2	xx (xx%)	xx (xx%)	xx (xx%)
2-4	xx (xx%)	xx (xx%)	xx (xx%)
4-8	xx (xx%)	xx (xx%)	xx (xx%)
8-12	xx (xx%)	xx (xx%)	xx (xx%)
>12	xx (xx%)	xx (xx%)	xx (xx%)
	xx (xx%)	xx (xx%)	xx (xx%)

#### 9.3.2 Adverse Events

Since in each part of this study, surveillance of adverse events (AE) will begin from the time the subject receives study treatment until the end of the study, all AEs in this study are considered treatment-emergent AEs (TEAEs). The TEAEs verbatim text recorded in the data base will be coded to associate MedDRA System Organ Classes (SOCs) and preferred term (PT).

TEAEs will be listed and summarized as follows.

Listing of Subject Numbers for Adverse Events

SYSTEM ORGAN CLASS Preferred Term	TREATMENT	NO. WITH EVENT	SUBJECT NUMBERS
SOC1 Preferred term a	Placebo Leronlimab 700 mg	3 2	xxx, xxx, xxx xxx, xxx

	STATISTICAL ANALYSIS PLAN (SAP) CD1-NASH-01		
	Protocol No. CD1-NASH-01	Revision No. Rev. 00	Effective Date: 17-Dec-2021

	Leronlimab 350 mg	1	xxx
Preferred term b	Placebo	3	xxx, xxx, xxx
	Leronlimab 700 mg	2	xxx, xxx
	Leronlimab 350 mg	1	xxx

#### Listing of Relationship of Adverse Event SOCs, and Verbatim Text

SYSTEM ORGAN CLASS	PREFERRED TERM	VERBATIM TEXT
SOC1	xxxxxx xxxxxxxx xxxxxx xxxx	xxxxxxxx xxxxxxxx xxxxxxxxxxxx
SOC 2	xxxxxx xxxxxxxx xxxxxx xxxx xxxxxx	xxxxxxxx xxxxxxxx xxxxxxxxxxxx xxxxxxxx

#### Adverse Event Subject Listings

Subject listings of adverse events will be sorted by treatment, subject number, SOC and PT will be provided and will display the following variables:

- Treatment group
- Subject Number
- System Organ Class (SOC)
- Preferred Term (PT)
- CTCAE Intensity Grade Assessment (1-5)
- Relationship to study treatment (Causality: Unrelated, Unlikely, Possibly, probably, Definitely)
- Treatment given to treat the event
- Outcome (fatal, not recovered/not resolved, recovered/resolved, recovered/resolved with sequalae, recovering/resolving, and unknown),
- Seriousness (Y/N)
- Impact (dose increased, dose not changed, dose reduced, drug interrupted, drug withdrawn, unknown, and not applicable)

Following subject listings will be produced:

- Subject listing of all adverse events
- Subject listing of fatal adverse events
- Subject listing of non-fatal adverse events
- Subject listing of adverse events of special interest (injection site reaction)
- Subject listing of serious adverse events
- Subject listing of adverse events leading to withdrawal

#### Subject Listing of All Adverse Events\*

## STATISTICAL ANALYSIS PLAN (SAP) CD1-NASH-01

Protocol No. CD1-NASH-01      Revision No. Rev. 00      Effective Date: 17-Dec-2021

Treatment: Placebo\*

Subject	Age	Preferred term/ Verbatim text	Outcome/ Onset date/ Resolution date	Time since 1 st dose/ Time since last dose	Intensity/ Seriousness/ Withdrawal	Action taken/ Relationship to Study drug
xxx	xxxx/ xxx/ xxxx/ xxxx	xxxxxxxxxx/ xxxxxxxxxx	xxx/ xxx/ xxxxx	xxxxx xxxxx xxxx	xxxxx/ xxxx/ xxxx	xxxxx/ xxxxxxxx
xxx	xxxx/ xxx/ xxxx/ xxxx	xxxxxxxxxx/ xxxxxxxxxx	xxx/ xxx/ xxxxx	xxxxx xxxxx xxxx	xxxxx/ xxxx/ xxxx	xxxxx/ xxxxxxxx

*\*Programming note: Repeat for fatal, non-fatal, events of special interest, serious and adverse events leading to withdrawal*

### Adverse Event Summaries

For the purposes of summarizing the TEAEs, the adverse event summaries will be sorted by MedDRA System Organ Classes (SOCs), in descending order from the SOC with the highest total incidence (i.e., summed across all treatment groups) for any adverse event within the class to the SOC with the lowest total incidence. Within each level, adverse events will be presented in descending order from the adverse event with the highest total incidence to the lowest total incidence. If the total incidence for any two or more adverse events is equal, the events will be presented in alphabetical order. Levels will not be presented if no adverse events occur within the level.

The following TEAE summaries will be provided:

- Summary of all adverse events
- Summary of drug-related adverse events
- Summary of serious adverse events
- Summary of adverse events leading to withdrawal

### Summary of All Adverse Events\*

	PLACEBO (N=X)	PART 1 LERONLIMAB 700 MG (N=XX)	PART 2 LERONLIMAB 350MG (N=XX)
ANY EVENT	n (xx%)	n (xx%)	n (xx%)
SOC	n (xx%)	n (xx%)	n (xx%)
Any event	n (xx%)	n (xx%)	n (xx%)
PT 1	n (xx%)	n (xx%)	n (xx%)
PT 2	n (xx%)	n (xx%)	n (xx%)

## STATISTICAL ANALYSIS PLAN (SAP) CD1-NASH-01

Protocol No. CD1-NASH-01	Revision No. Rev. 00	Effective Date: 17-Dec-2021
-----------------------------	-------------------------	--------------------------------

*\*Programming note: Repeat for drug-related, serious and events leading to withdrawal.*

### 9.3.3 Clinical Laboratory Assessments

All laboratory values Including Height, Weight and BMI will be listed. These variables will also be summarized as continuous variable and presented by treatment group and time point. For the purpose of this study, the below baseline (normal) values/reference range for the liver function panel be flagged:

Total Bilirubin	0.2-0.9 mg/dl
Direct Bilirubin	0.0 – 0.2 mg/dl
SGOT (AST)	15-41 IU/L
SGPT (ALT)	M: 17-63 IU/L; F: 14-54 IU/L
Alkaline Phosphatase (ALP)	34-104 IU/L

#### Subject listing of Clinical Laboratory Data:

##### Part 1, Treatment: Placebo

Subject	Age	Lab test (Units)	Visit	Value	Normal range	Flag
	Sex					
	Race					
	Weight					
xxx						

---

Normal range flag: H=above range, L=below range.

#### Subject Listing of Height, Weight, and BMI

Treat- ment	Investi- gator	Subject	Visit	Height	Weight	BMI
Part 1	Placebo					
	Leronlimab 700 mg					
Part 2	Leronlimab 350 mg					

The clinical laboratories at every assessed time point and changes from baseline will be summarised using the minimum set of summary statistics n, mean, SD, Median, Min and Max

#### Summary of Laboratory Data

##### Laboratory: xxxxx\*

Treatment	N	Visit	n	Mean	SD	Median	Min	Max
Part 1	Placebo							

## STATISTICAL ANALYSIS PLAN (SAP) CD1-NASH-01

Protocol No. CD1-NASH-01	Revision No. Rev. 00	Effective Date: 17-Dec-2021
-----------------------------	-------------------------	--------------------------------

Part 2      Leronlimab  
350 mg

*\*Programming note: Repeat for all labs*

### 9.3.4 Physical Examination

Subject-listing of abnormalities noted during physical examination including Weight will be presented.

#### Listing of Abnormalities in Physical Examination

TREAT- MENT	INVESTI- GATOR	SUBJECT	VISIT	ABNORMALITY
Part 1      Placebo Leronlimab 700 mg				
Part 2      Leronlimab 350 mg				

### 9.3.5 Vital Signs

Subject-listing of vital signs will be presented.

#### Subject Listing of Vital Signs

Treatment	Inv.	Subj.	Age(y)/ Sex/ Race	Visit	Systolic BP (mmHg)	Diastolic BP (mmHg)	Vital Sign 3 (units)
Part 1      Placebo	xx	xx	23/ Male/ White	xx xx xx	xx H xx xx	xx L xx xx H	x H xx H xx

The vital signs at every assessed time point and changes from baseline will be summarised using the minimum set of summary statistics n, mean, SD, Median, min and max.

#### Summary of Systolic BP (mmHg)\*

Treatment	N	Visit	n	Mean	SD	Median	Min	Max
Part 1      Placebo Leronlimab 700 mg								
Part 2      Leronlimab 350 mg								

*\*Programming note: Repeat for Diastolic BP (mmHG) and Heart Rate*

	STATISTICAL ANALYSIS PLAN (SAP) CD1-NASH-01		
	Protocol No. CD1-NASH-01	Revision No. Rev. 00	Effective Date: 17-Dec-2021

### 9.3.6 Electrocardiogram (ECG)

Ventricular rate (beats per minute), PR interval (msec), QRS interval (msec), QT interval (msec), and QTc interval (msec). Additionally, the Investigator will record the overall results of the ECG reading as either normal or abnormal, and as either not clinically significant or clinically significant. If abnormalities are observed, each will be recorded. Subject-listing of ECG values will be presented.

The ECG at each assessed time point and changes from baseline will be summarised using the minimum set of summary statistics n, mean, SD, Median, Minimum and maximum

#### Summary of Ventricular rate (beats per minute)

	Treatment	N	Visit	n	Mean	SD	Median	Min	Max
Part 1	Placebo								
	Leronlimab								
	700 mg								
Part 2	Leronlimab								
	350 mg								

*\*Programming note: Repeat for PR interval (msec) QRS interval (msec), QT interval (msec), and QTc interval (msec).*

#### Summary of Overall Result of 12-Lead ECG

	TREAT- MENT	VISIT	NORMAL	ABNORMAL	CLINICALLY NOT SIGNIFICANT	CLINICALLY SIGNIFICANT
Part 1	Placebo	xx	xx (xx)	xx (xx)	xx (xx)	xx (xx)
	Leronlimab	xx	xx (xx)	xx (xx)	xx (xx)	xx (xx)
	700 mg					
Part 2	Leronlimab	xx	xx (xx)	xx (xx)	xx (xx)	xx (xx)
	350 mg					

### 9.3.7 Tolerability

Tolerability of repeated injections will be assessed by

- Subject rated 11-point Numeric Pain Rating Scale (0=None to 10=Worse)
- Investigator-evaluation of injection site reactions

#### *Subject Injection Site Pain Rating Score*

A subject listing of pain score will be presented.

The frequencies of subject rated pain score will be computed

## STATISTICAL ANALYSIS PLAN (SAP) CD1-NASH-01

Protocol No. CD1-NASH-01	Revision No. Rev. 00	Effective Date: 17-Dec-2021
-----------------------------	-------------------------	--------------------------------

### Summary of Inject Site Pain Score N (%)

Severity[1]	Placebo (N=nn)	Leronlimab 700 mg (N=nn)	Leronlimab 350 mg (N=nn)
0-5	xx (%)	xx (%)	xx (%)
6-7	xx (%)	xx (%)	xx (%)
8-10	xx (%)	xx (%)	xx (%)

[1] 0=None to 10=Worse.

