2 STUDY OBJECTIVES

2.1 PRIMARY OBJECTIVE:

- The Primary objective of this study is to assess the efficacy of Leronlimab (PRO 140) in improving liver function in adult patients diagnosed with NASH compared to placebo

2.2 SECONDARY OBJECTIVE:

- The Secondary objective of this study is to assess the safety and tolerability of Leronlimab (PRO 140) in adult patients diagnosed with NASH compared to placebo

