7.12 PAIN SEVERITY ASSESSMENT

Tolerability of repeated subcutaneous administration of Leronlimab (PRO 140) is evaluated based on assessment of subject-perceived injection site pain using 11-point Numeric Pain Rating Scale.

Before each study treatment administration (T2 to T13, and at EOT), subjects will be asked to evaluate the pain intensity **over the past week** at the site of injection administration based on 11-point Numeric Rating Scale from 0 to 10. “0” meaning “no pain” and “10” meaning “worst possible pain”.

Figure 7-1: 11-Point Numeric Pain Rating Scale

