- by SOC and PT
- by SOC, PT, and severity

- by SOC, PT, and relationship to study drug

Clinical Laboratory Data

All laboratory values will be listed. Laboratory measurements will also be summarized as continuous variable and presented by treatment group and time point.

Physical Examination

All physical examination findings will be listed and/or summarized.

Vital Signs

All vital sign findings will be listed and summarized.

Electrocardiograms (ECGs)

All ECG findings will be listed and summarized.

Tolerability

Pain severity assessment (using 11-point Numeric Pain Rating Scale) and injection site reactions will be listed and summarized.

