## 2 PROTOCOL DESIGN AND OBJECTIVES

### 2.1 Study Objectives

Primary Objective:

- The Primary objective of this study is to assess the efficacy of Leronlimab (PRO 140) in improving liver function in adult patients diagnosed with NASH compared to placebo

Secondary Objective:

- The Secondary objective of this study is to assess the safety and tolerability of Leronlimab (PRO 140) in adult patients diagnosed with NASH compared to placebo

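### The SAP's only pain-specific table puts scores 0 to 5 in one row and names no counting unit or visit, so differences between arms within 0 to 5 cannot be seen in it

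*SAP*

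**What the plan says.** The secondary objective in Protocol 2.2 is "to assess the safety and tolerability of Leronlimab (PRO 140) in adult patients diagnosed with NASH compared to placebo"; SAP 2.1 repeats it. SAP 3.4 and 9.3.7 name two tolerability measures: the subject's own 0-10 pain rating and the investigator's evaluation of injection site reactions.

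On collection, Protocol 7.12 says: "Before each study treatment administration (T2 to T13, and at EOT), subjects will be asked to evaluate the pain intensity". The rating refers to the week just past.

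On analysis, Protocol 8.8 says: "Pain severity assessment (using 11-point Numeric Pain Rating Scale) and injection site reactions will be listed and summarized". SAP 9.3.7 adds two sentences, "A subject listing of pain score will be presented" and "The frequencies of subject rated pain score will be computed", and then the table "Summary of Inject Site Pain Score". That table has rows 0-5, 6-7 and 8-10, a count and percentage for each of the three groups, and a footnote defining 0 as none. It has no visit row or column, gives no rule for reducing repeated scores to one, and offers no reason for the cut-points.

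**The concern.** A frequency table shows a difference between arms only if subjects fall in different rows. Here the widest row sits at the bottom of the scale and includes zero. If scores in both arms stay at 5 or below, the table shows about 100% against 100% whatever the arms did. The absence of a counting unit is a separate problem: two programmers could follow the SAP faithfully and produce different tables.

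At stake is the reporting of one of the two named tolerability measures against placebo. No test of pain is planned and no efficacy conclusion depends on it.

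**Working it through.** There is no planned figure to reproduce. The documents give no expected pain distribution, SD or power for this measure.

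**1. Scale points per row.** The scale has 11 points, 0 to 10.

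- 0-5: 6/11 = 55%
- 6-7: 2/11 = 18%
- 8-10: 3/11 = 27%

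**2. A check that needs no distribution.** Suppose every score is 0 in one arm and 5 in the other. Both arms show 100% in the first row, although the means differ by 5 points.

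**3. Scores available.** T2 to T13 is 12 visits, and EOT makes 13. With 30 subjects per arm that is up to 30 × 13 = 390 scores per arm. The percentage base could therefore be about 30 subjects or up to 390 assessments, and the table does not say which.

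**4. Illustration of how much is hidden.** All inputs are assumptions: one score per subject, from a normal variable with mean μ and SD σ, rounded and clipped to 0-10. Then P(score ≤ 5) = Φ((5.5 − μ)/σ) and P(score = 0) = Φ((0.5 − μ)/σ). For example, with μ = 3 and σ = 1.5, P(≤ 5) = Φ(1.67) = 95.2% and P(0) = Φ(−1.67) = 5%.

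| σ | μ, two arms | Mean after rounding and clipping | In 0-5 row | Score 0 | Expected above 5, of 30 |
|---|---|---|---|---|---|
| 1.5 | 1 vs 2 | 1.22 vs 2.06 | 99.9% vs 99.0% | 37% vs 16% | 0.04 vs 0.29 |
| 2.0 | 1 vs 2 | 1.39 vs 2.16 | 98.8% vs 96.0% | 40% vs 23% | 0.37 vs 1.20 |
| 1.5 | 1 vs 3 | 1.22 vs 3.01 | 99.9% vs 95.2% | 37% vs 5% | 0.04 vs 1.43 |
| 2.0 | 1 vs 3 | 1.39 vs 3.06 | 98.8% vs 89.4% | 40% vs 11% | 0.37 vs 3.17 |
| 1.5 | 2 vs 4 | 2.06 vs 4.00 | 99.0% vs 84.1% | 16% vs 1% | 0.29 vs 4.76 |
| 2.0 | 2 vs 4 | 2.16 vs 4.02 | 96.0% vs 77.3% | 23% vs 4% | 1.20 vs 6.80 |

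In the first line the table shows almost nothing while the pain-free share falls by more than half. In the last line a difference is plain even with these bins.

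**5. Effect of the counting unit.** Take μ = 2, σ = 1.5, where a single score is in the 0-5 row with probability 0.990. If the table counts each subject's worst of 13 scores, the row holds 0.990^13 = 88% when scores are independent, rising towards 99% as they become fully correlated. The same data can thus print as anything from 88% to 99% depending on an unstated choice.

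**6. Comparison with other safety measures.** For laboratory values (SAP 9.3.3), vital signs (9.3.5) and ECG (9.3.6), the SAP asks for n, mean, SD, median, minimum and maximum at each assessed time point. For pain it asks for a listing and frequencies only.

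**The case against.** The strongest reply is that the table is not the whole plan. The sentence on frequencies names no bins and could mean a count for each score. SAP 9.1 requires mean, SD and median by group for continuous variables, which might cover a 0-10 score. SAP 9.1.1 leaves table formats to a separate shell document, which is not available here. Injection site reactions are also graded, listed, and reported among the adverse events by arm. The trial is sized for descriptive results.

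Part of this stands. The individual scores will be listed, so this is a gap in reporting and not a loss of data. The rest does not close the gap. The SAP never classes pain as continuous, and where it wants those statistics for other safety measures it says so. The table that follows the frequency sentence is binned. A listing of up to 90 × 13 = 1,170 scores is not a comparison with placebo. Graded reactions are the investigator's measure, and the SAP names the subject's rating separately.

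A reader might also infer three stronger things that the documents do not support:

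- That the objective concerns mild-to-moderate pain in particular. It names safety and tolerability against placebo, and no passage attaches such a label to scores 0-5.
- That nearly all scores will fall in the first row because earlier studies reported mostly mild injection site reactions. Those statements describe graded adverse events, and nothing maps them to a pain score.
- That the table counts each subject once. The N (%) heading suggests it, but the SAP does not say so.

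**Conclusion.** The point holds as a minor reporting defect. That differences within 0-5 cannot be seen in the table follows from the row limits alone and needs no assumption. The missing visit dimension and counting unit are likewise plain from SAP 9.3.7.

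The size is not known. It would go too far to say that the table will show no difference between arms: that needs scores to stay at or below 5. The illustrations run from a 0.9-point gap in the first row (99.9% vs 99.0%) to an 18.7-point gap (96.0% vs 77.3%). All of them rest on assumed rounded-normal scores, one per subject, and should not be read as forecasts.

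**What to change.** In SAP 9.3.7, before database lock:

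- State the counting unit, for example each subject's worst score after the first dose, and label the percentage base accordingly.
- Add n, mean, SD, median, minimum and maximum of the pain score by visit and arm, as is already done for laboratory values, vital signs and ECG.
- Show score 0 in its own row and split 1-5, or give a count for each score. The present 6-7 and 8-10 rows can stay. The split of 1-5 is a matter of preference, since the documents support no particular cut-points; counts for each score avoid the choice.

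The cost is one revised table shell and slightly more output. No new data are needed.
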